3.1.6 Stage 2 subgroup analysis for primary outcome

Subgroup analysis will be performed for the primary outcome for the final analysis only to explore the uniformity of the treatment effect. The following subgroups will be examined by adding a treatment-by-subgroup interaction term to the same analysis model as for the primary outcome:

- Sex: male vs female;
- Age: <65 years vs ≥65 years
- Obesity: $<25, 25-29.9, \ge 30$
- Chronic heart disease: yes vs no;
- Lung disease: yes vs no;
- Kidney disease: yes vs no;
- Liver disease: yes vs no;
- Diabetes: yes vs no;
- Immunocompromised: yes vs no;
- Smoking status: current vs non-smoker;
- CRP > 200mg/L: yes vs no and/or D-dimer >2500mg/mL: yes vs no;
- Time since onset of symptoms:0-5, 6-10, >10 days prior to randomisation

P-values for each interaction term will be presented. No adjustment for multiple tests will be made and the results will be viewed as hypothesis generating only. The consistency of estimates will be depicted visually by means of a forest plot.

3.2 Secondary outcomes of the main study

Analysis of the secondary outcomes listed below will be undertaken for the final analysis only. Each of the outcomes will be examined at 14 and 28 days and comparisons will be between RUX or FOS versus SOC:

- Change in severity on the modified WHO COVID-19 Ordinal Scale (3 or 4 to 5,6,7,8,9)
- Death (yes/no)
- Invasive ventilation (yes/no)
- ECMO (yes/no)
- Non-invasive ventilation including CPAP and high flow nasal oxygen (yes/no)
- Renal replacement therapy (yes/no)
- Venous thromboembolism (yes/no)
- Inflammatory markers CRP, LDH, ferritin, D-dimer (units)

- Length of stay (days)
- o Serum creatinine

3.2.1 Severe COVID-19 within 28 days

The proportion of participants progressing from mild to severe COVID-19 pneumonia within 28 days will be analysed using the main analysis model as described in section 3.1.3, replacing the 14 day outcome with the 28 day outcome.

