In Stage 2 a logistic regression model will be used to assess the treatment effect of RUX and FOS compared to SOC. The model will include the treatment arms, baseline modified WHO Severity Score, trial co-enrolment at baseline, and randomisation stratification variables viz. site and age (<65 vs ≥65). As well as reporting OR and 95% CIs, the model will be used to estimate the difference in proportion of participants with modified WHO COVID-19 Ordinal Score ≥5. The treatment effect in the absence of post-randomisation co-enrolment and receipt of rescue medication will be estimated in a supplementary analysis where participants' outcomes after either will be treated as missing and a controlled multiple imputation using a delta based approach will be used.

For the primary outcome, progression to severe COVID-19 disease within 14 days, discharge alive from the admitting hospital before 14 days will assume safety from the event (in the absence of additional data confirming otherwise). An additional sensitivity analysis will be performed if there is a change of dose after review of the first thirty patients.

For time-to-event analyses required for secondary endpoints such as time to discharge, each treatment group will be compared with SOC and modelled using a proportional hazards time-to-event model adjusted for randomisation stratification variables. Kaplan-Meier estimates for the time to event will also be plotted (with confidence intervals). The log-rank 'observed minus expected' statistic (and its variance) will be used to estimate the average event rate ratio (and its confidence interval) for those allocated to each treatment group versus the no additional treatment group.

Pre-specified subgroup analysis will be conducted for the primary outcome using the statistical test for interaction (or test for trend where appropriate) for the following: disease severity as graded by the WHO

MATIS version 4.0 dated 2nd November 2022

IRAS: 282552 Page **28** of **57** 

Imperial College Healthcare

COVID-19 Ordinal Severity Scale; time since onset of symptoms; sex; age; and comorbidities obesity, chronic heart, lung, kidney and liver disease, diabetes, immunocompromised and smoking status. Pre-specified subgroup analyses will also be conducted for the primary outcome using the statistical test for interaction (or test for trend where appropriate) for patients with admission CRP >200mg/L and/or D-dimer 2500ng/mL.

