Every effort will be made to obtain follow-up data for all participants including those that stop treatment. The number and proportion of participants missing WHO COVID-19 status by treatment group and visit will be tabulated (see section 2.5 above). For participants who are discharged early the assumption will be made that they did not progress to grade 5 WHO scale. If there is a >5% rate of missing outcomes after this, we will impute missing WHO COVID-19 data in the primary analysis model using multiple imputation under the assumption of missing at random (MAR). That is the probability of being missing is not dependent on the values of unobserved data, conditional on the observed values of the variables included in the analysis model. Imputation under MAR using chained equations following the guidance of White et al. will be undertaken.⁴ Variables in the imputation model will include the variables in the primary analysis model described above plus baseline WHO COVID-19 score (3 or 4), age (<65 or ≥65), receipt of dexamethasone and/or tociluzimab at the time of or prior to randomisation into MATIS. Additional auxiliary variables that are suspected to be associated with the outcome and are predictors of missingness will also be included. These are receipt of any effective treatments post randomisation as a result of co-enrolment when occurring postrandomisation, and receipt of known effective treatments dexamethasone and tociluzimab postrandomisation (>1 day post randomisation) and WHO COVID-19 scores at day 1 and day 7. Using White et al.'s rule of thumb we will impute m datasets based on the percentage of participants with incomplete outcomes, where m will be rounded to the nearest 10, for example if 8% of participants have incomplete primary outcome then m=10 will be used.

Before undertaking the multiple imputation as described above we will impute any missing baseline data deterministically only using other baseline data, this includes the baseline WHO COVID-19 status, age, receipt of dexamethasone and/or tociluzimab at the time of or prior to randomisation into MATIS. To do this we will impute missing values with the mean values of observed data. In line with White et al., outcomes will be imputed separately for each treatment group.

Imputed datasets will then be analysed using the primary analysis model described above.

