 FOS_{ij} : dummy variable for treatment ($FOS_{ij} = 0$ or 1) for participant i in jth site

 WHO_{ij}^0 : dummy variable for baseline WHO COVID-19 value for participant i in jth site (WHO_{ij})

0 or 1 where 0 indicates score of 3 and 1 indicates score of 4)

 AGE_{ij}^{0} : dummy variable for age-group ($AGE_{ij} = 0$ or 1 where 0 indicates <

65 years and 1 indicates \geq 65) for participant i

 DEX_{ij}^0 : dummy variable for receipt of dexamethasone at the time of or prior to randomisation (includes day of randomisation or one day post randomisation) ($DEX_{ij} = 0$ or 1) for participant i

 TOC_{ij}^0 : dummy variable for receipt of tociluzimab at the time of or prior to randomisation (includes

day of randomisation or one day post randomisation) ($TOC_{ij} = 0$ or 1) for participant i

 VAC_{ij}^0 : dummy variable for prior vaccination against COVID-19 at the time of or prior to randomisation (includes day of randomisation or one day post randomisation) ($VAC_{ij} = 0 \ or \ 1$) for participant i

 PAX_{ij}^0 : dummy variable for receipt of paxlovid at the time of or prior to randomisation (includes day of randomisation or one day post randomisation) ($PAX_{ij} = 0 \text{ or } 1$) for participant i

 MOL_{ij}^0 : dummy variable for receipt of molnupiravir at the time of or prior to randomisation (includes day of randomisation or one day post randomisation) ($MOL_{ij} = 0$ or 1) for participant i $Site_j$: dummy variable for each of the jth sites

 π_{ij} : probability of WHO COVID-19 \geq 5 for the ith participant in jth site

To account for missing outcomes in the primary analysis model we will impute missing WHO COVID-19 status using multiple imputation under the assumption of missing at random (MAR) as described in the primary statistical model at stage 1 section 3.1.2 plus the imputation model will contain the following additional variables: prior vaccination against COVID-19, and receipt of paxlovid and/or molnupiravir at the time of or prior to randomisation into MATIS, plus post-randomisation receipt of paxlovid and/or molnupiravir. Multiple imputation will be used for the final analysis regardless of levels of missingness at this stage.

As well as reporting odds ratios and 95% CIs, the model will be used to estimate the difference in proportion of participants with modified WHO COVID-19 Ordinal Score ≥ 5 .

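### The 28-day severity analysis inherits an imputation model that leaves out day 14 status, so patients known to be event-free then are generally imputed with too high a risk (minor)

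*SAP*

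**What the plan says.** SAP 3.2.1 is one sentence. It applies the 3.1.3 model to 28-day severity, "replacing the 14 day outcome with the 28 day outcome". It adds nothing about missing data.

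SAP 3.1.3 always imputes at the final analysis: "Multiple imputation will be used for the final analysis regardless of levels of missingness at this stage". It takes the imputation model from 3.1.2, "as described in the primary statistical model at stage 1 section 3.1.2 plus the imputation model will contain the following additional variables". The additions are vaccination and antiviral variables. In 3.1.2 the only severity measures after baseline are "WHO COVID-19 scores at day 1 and day 7". The other predictors are the analysis-model covariates and active or rescue treatments received after randomisation, and "outcomes will be imputed separately for each treatment group".

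A deterministic rule comes before the imputation in 3.1.2: "For participants who are discharged early the assumption will be made that they did not progress to grade 5 WHO scale". The SAP gives no day limit for it. Protocol 4.2 does, for the primary outcome: "discharge alive from the admitting hospital before 14 days will assume safety from the event".

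SAP 3.2.3 also reuses the 3.1.3 model for the component outcomes, but states that those fits are complete-case without imputation. Section 3.2.1 has no such opt-out.

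**The concern.** When the 28-day outcome replaces the 14-day outcome, day 14 status stops being the outcome and does not become a predictor. Yet it is the most informative observation available. The outcome is cumulative, so severe by day 14 means severe by day 28. For someone event-free at day 14, only progression on days 15-28 remains uncertain.

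A model that sees severity only to day 7 gives that patient a risk covering days 8-28, including a week the patient is known to have passed without an event.

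The omission also sits badly with the SAP's own criteria. Section 3.1.2 seeks auxiliaries that relate to the outcome and predict missingness, and states missing at random conditional on the variables included. Day 14 status meets both criteria: anyone severe by day 14 has a known 28-day outcome, so whether that outcome can be missing depends on day 14 status.

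At stake are an upward shift in the 28-day proportions and, if missingness differs between arms, a shift in the odds ratio for this secondary outcome.

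**Working it through.** **Inputs.** The plan gives no figure for the 28-day imputation, so there is none to reproduce. It supplies the 14-day risks (50% control, 30% experimental, SAP 1.5.1) and a 5% allowance for missing outcomes (SAP 1.5.2). Risks at days 7 and 28 are assumptions.

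**Step 1: who is affected.** SAP 2.7 counts events at any point up to day 14, and again up to day 28. Patients severe by day 14 are therefore already 28-day events. Those imputed are either event-free at day 14 or also missing at day 14. Only the first group is affected.

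**Step 2: risk for one such patient.** True late risk is (p28 − p14)/(1 − p14). Imputed risk, given only event-free at day 7, is (p28 − p7)/(1 − p7).

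| Arm | p7/p14/p28 (assumed) | True | Imputed |
|---|---|---|---|
| SOC | 35/50/55% | 0.05/0.50 = 10% | 0.20/0.65 = 31% |
| Active | 20/30/33% | 0.03/0.70 = 4% | 0.13/0.80 = 16% |

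**Step 3: range.** Let p be the 14-day risk, s the share of 14-day events that occur by day 7, and h the late risk. Imputed risk is [p(1 − s) + (1 − p)h]/(1 − ps). With s = 0.8 and h = 5%:

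- control: (0.10 + 0.025)/0.60 = 20.8% against 5%
- experimental: (0.06 + 0.035)/0.76 = 12.5% against 5%

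Over s = 0.5 to 0.95 and h = 2% to 15%, the ratio runs from 1.3 to 17 in the control arm (excess 4 to 33 points) and from 1.1 to 9.6 in the experimental arm (excess 2 to 17 points).

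**Step 4: shift in an arm's proportion.** With a fraction m missing at day 28 regardless of status, the shift is m × (1 − p14) × (imputed − true). At m = 5% and the Step 2 risks:

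- SOC: 0.05 × 0.50 × 0.208 = 0.5 points
- active: 0.05 × 0.70 × 0.120 = 0.4 points

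If all 5% are event-free patients who do get imputed, the factor (1 − p14) drops out and the shifts are 1.0 and 0.6 points.

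**Step 5: odds ratio.** The true value is (0.33/0.67)/(0.55/0.45) = 0.403.

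| Missing, SOC / active | Odds ratio |
|---|---|
| 5% / 5% | 0.402 |
| 10% / 10% | 0.401 |
| 15% / 5% | 0.386 |
| 5% / 15% | 0.417 |

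The unequal splits are illustrations without a source in the documents. With 152 per arm, the standard error of the log odds ratio is √[1/(152 × 0.55 × 0.45) + 1/(152 × 0.33 × 0.67)] = 0.24. The two unequal cases move the log odds ratio by 0.04 and 0.03, under 0.2 standard errors.

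**Step 6: simulation check.** A large-sample, per-arm logistic imputation used baseline score, age, dexamethasone, day 7 score and post-randomisation rescue as predictors, with 5% of the arm imputed. Assumptions: 60-90% of 14-day events by day 7, 70% of event-free patients discharged by day 14, late risk 5-20% in in-patients and 2-5% after discharge.

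- Any event-free patient may be missing: control imputed 12-24% against true 3-7%; experimental 8-15% against 3-7%.
- Only patients still in hospital at day 14 are missing: control imputed 18-38% against 5-22%. With 90% of events by day 7 and 20% late risk the excess is gone: 20.4% against 20.7% (control) and 15.2% against 19.6% (experimental).
- Across all scenarios an arm's proportion shifts by −0.2 to +1.6 points, and the arm difference by +0.2 to +0.7 points, towards the drug.

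**Step 7: does day 14 information repair it?** When any event-free patient may be missing, restricting imputation to patients event-free at day 14 gave 2.9-7.6% against true 2.8-7.4%. When only in-patients are missing, severe status at day 14 alone under-imputes (for example 4.8% against 9.7%), so hospital status is needed too.

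**The case against.** The strongest reply is the early-discharge rule. The cross-reference that brings imputation into 3.2.1 also brings in the preceding step, which sets patients discharged early to non-severe. With 28 substituted for 14 days, early could mean before day 28. Visits after discharge are not mandated (protocol Table 7 footnote), so the typical patient seen event-free at day 14 and missing at day 28 has probably been discharged. On that reading most affected patients never reach the imputation, and those left are mainly higher-risk in-patients, for whom the excess can shrink or reverse. This stands as far as it goes. But the protocol limits the rule to discharge before day 14, and the SAP does not say which limit applies at day 28.

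Three further points also stand. It would be wrong to infer that the imputation uses nothing after day 7, because treatments received after randomisation are predictors with no day 7 cut-off. Patients severe by day 14 are already 28-day events under the cumulative definition. And imputation at day 28 rests on a cross-reference, although the explicit opt-out in 3.2.3 implies that the 3.1.3 model otherwise carries it.

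None of this supplies the missing predictor. Rescue treatment was in the Step 6 model, and the excess remained in most scenarios.

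**Conclusion.** The point holds as a minor one. As written, the 28-day imputation ignores day 14 status that the trial records, and a patient otherwise typical of those event-free at day 14 is imputed with too high a risk. The direction follows from the structure; the size does not, because the documents do not say how events split between days 1-7, 8-14 and 15-28.

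A reader might infer that such patients are imputed as severe far too often, or that the 28-day odds ratio is materially biased. The documents do not support either. The per-patient ratio can be as low as about 1.1, and the excess can vanish or reverse if only higher-risk in-patients are missing. At the 5% missingness the plan allows for, the shift in an arm's proportion is about 0.5 points under the 35/50/55% and 20/30/33% assumptions, and at most 1.6 points in the simulations. The odds ratio barely moves unless missingness differs by arm. The outcome is secondary and lies outside the one-sided 0.027 test of the primary outcome.

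**What to change.** Add to SAP 3.2.1:

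- For the 28-day outcome, the imputation model also includes severe status by day 14, the day 14 WHO score, and hospital or discharge status at day 14. Where a patient is known to be event-free at day 14, only progression between days 14 and 28 is imputed.
- State that anyone recorded as severe by day 14 counts as severe by day 28. This follows from the cumulative definition but is worth writing down.
- State whether the early-discharge assumption extends to discharge before day 28 or stops at day 14 as in protocol 4.2.

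Two practical notes. Severe status by day 14 predicts the 28-day outcome perfectly, so the late-progression step is best fitted among patients event-free at day 14, with day 14 status imputed first where it is missing. Late events would also be few: under the assumed risks, 152 × 0.05 = 7.6 in SOC and 152 × 0.03 = 4.6 in an active arm. With imputation done separately by arm, the SAP should say how the predictor list is shortened if that step is unstable.

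The cost is a few sentences and a small change to the analysis code. No new data are needed, since day 14 assessments and discharge dates are already collected.

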3.2.2 Modified WHO COVID-19 score

A mixed effects ordered logistic regression will be used to estimate the odds ratio of disease severity as measured by the modified WHO COVID-19 (ordinal scale) over time by treatment arm. Specifically a generalized linear model with modified WHO COVID-19 status (scores 3/4 through to 9) as the outcome (ordered categorical variable) with S ordinal categories s (s=3/4, 5, 6, 7, 8, 9) and treatment group, time, time-by-treatment arm interaction, baseline WHO COVID-19 score (3 or 4), age (<65 or \geq 65), receipt of known effective treatments dexamethasone and/or tociluzimab, prior vaccination against COVID-19, and receipt of paxlovid and/or molnupiravir at the time of or prior to randomisation into MATIS as covariates will be fitted. Participants will be included as a random intercept (ζ_{ij}). Given the anticipated small number of sites in this study, site will be included in the model as a fixed effect. The model will be fitted using the *ologit* link function (or the *meologit* command) in Stata and the treatment effect will be reported as an odds ratio with corresponding 95% confidence intervals.

The model to be fitted will be:

$$\begin{split} logit \big(pr(\pi_{ij} > s) \big) \\ &= \beta_1 RUX_{ij} + \beta_2 FOS_{ij} + \beta_3 WHO_{ij}^0 + \beta_4 AGE_{ij}^0 + \beta_5 DEX_{ij}^0 + \beta_6 TOC_{ij}^0 \\ &+ \beta_7 VAC_{ij}^0 + \beta_8 PAX_{ij}^0 + \beta_9 MOL_{ij}^0 + \beta_{10} SITE_1 + \beta_{11} SITE_2 + \cdots \\ &+ \beta_{12} SITE_{j-1} + \beta_{13} time_7 + \beta_{14} time_{14} + \beta_{15} RUX_{ij} * time_7 + \beta_{16} RUX_{ij} \\ &* time_{14} + \beta_{17} FOS_{ij} * time_7 + \beta_{18} FOS_{ij} * time_{14} + \zeta_{ij} - \kappa_s \end{split}$$

 RUX_{ij} : dummy variable for treatment ($RUX_{ij} = 0$ or 1) for participant i in jth site FOS_{ij} : dummy variable for treatment ($FOS_{ij} = 0$ or 1) for participant i in jth site WHO_{ij}^0 : dummy variable for baseline WHO COVID-19 value for participant i in jth site ($WHO_{ij} = 0$ or 1 where 0 indicates score of 3 and 1 indicates score of 4)

 AGE_{ij}^0 : dummy variable for age-group ($AGE_{ij} = 0$ or 1 where 0 indicates < 65 years and 1 indicates \geq 65) for participant i

 DEX_{ij}^0 : dummy variable for receipt of dexamethasone at the time of or prior to randomisation (includes day of randomisation or one day post randomisation) ($DEX_{ij} = 0 \text{ or } 1$) for participant i TOC_{ij}^0 : dummy variable for receipt of toczulimab at the time of or prior to randomisation (includes day of randomisation or one day post randomisation) ($TOC_{ij} = 0 \text{ or } 1$) for participant i VAC_{ij}^0 : dummy variable for prior vaccination against COVID-19 at the time of or prior to randomisation (includes day of randomisation or one day post randomisation) ($VAC_{ij} = 0 \text{ or } 1$) for participant i

 PAX_{ij}^0 : dummy variable for receipt of paxlovid at the time of or prior to randomisation (includes day of randomisation or one day post randomisation) ($PAX_{ij} = 0$ or 1) for participant i

 MOL_{ij}^0 : dummy variable for receipt of molnupiravir at the time of or prior to randomisation (includes day of randomisation or one day post randomisation) ($MOL_{ij} = 0$ or 1) for participant i

 $Site_i$: dummy variable for each of the jth sites

 $time_x$: dummy variable for time (= 0 or 1) at time point x days. Day 1 is represented by $time_7 = 0$ and $time_{14} = 0$

 $\zeta_{ij} \sim N(0, \sigma^2)$: participant specific random intercept

 κ_s : indicates the $\kappa_1, \kappa_{2,...} \kappa_{S-1}$ cut-points for each of the possible S outcomes of the WHO COVID-19 ordinal scale

 $(pr(\pi_{ij} > s))$: cumulative probability of the response being in a category higher than s π_{ij} : is the odds ratio of more severe versus less severe illness (regardless of where the ordinal scale is cut)

The model will be modified in a similar manner as the primary outcome modelling in the event of low event rates.

This analysis will be repeated on the original WHO COVID-19 (ordinal scale).

3.2.3 Components of the modified WHO COVID-19 score

The following outcomes will be examined at day 14 and day 28 by replacing the primary outcome in the main analysis model as described in section 3.1.3:

- Death (yes/no)
- Requirement for invasive ventilation plus organ support (yes/no)
- Invasive ventilation (yes/no)

- Non-invasive ventilation including CPAP and high flow nasal oxygen (yes/no)
- Renal replacement therapy (yes/no)
- Venous thromboembolism (yes/no)

Each model will be fitted on complete cases and no imputation of missing values or sensitivity analysis will be undertaken.

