#### 2 STUDY OBJECTIVES

#### 2.1 PRIMARY OBJECTIVE

The primary objective is to determine the efficacy of RUX and FOS to reduce the proportion of hospitalised patients progressing from mild/moderate to severe COVID-19 pneumonia. A modified WHO COVID-19 Severity Ordinal Scale (COVID-19 Therapeutic Trial Synopsis published 18th February 2020) will be used to grade clinical deterioration from Hospitalised Mild Disease (<5) to Hospitalised Severe Disease (≥ 5). The modification includes an additional grade for Hospitalised Severe Disease that allows the capture of clinical deterioration in patients for whom escalation in organ support is not offered. Patients are eligible for recruitment to MATIS at grades 3 or 4. These patients stand to gain the greatest benefit from inflammatory signal inhibitors that may ameliorate the cytokine storm and prevent organ failure.

Table 1. Modified WHO COVID-19 Severity Scale, from the WHO R&D Blueprint

Patient state Descriptor		Grade
Uninfected	No clinical or virological evidence of infection	0
Ambulatory	No limitation of activities	1

MATIS version 4.0 dated 2nd November 2022

IRAS: 282552 Page **20** of **57** 

	Limitation of activities	2
Haspitalisad mild disease	Hospitalised, no oxygen therapy	3
Hospitalised mild disease	Oxygen by mask or nasal prongs	4
	$SpO_2$ < 90% on $FiO_2$ $\geq$ 60% by face mask	5
Hospitalised severe disease	Non-invasive ventilation, CPAP or high-flow oxygen	6
	Intubation and mechanical ventilation	7
	Ventilation + additional organ support (vasopressors, RRT, ECMO)	8
Dead	Death	9

Published in the COVID Therapeutic Trial Synopsis, February 18th 2020

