#### 2.2 SECONDARY OBJECTIVES

- Determine the efficacy of RUX or FOS to reduce mortality
- Determine the efficacy of RUX or FOS to reduce the need for invasive ventilation and/or ECMO
- Determine the efficacy of RUX or FOS to reduce the need for non-invasive ventilation including CPAP or high flow nasal oxygen
- Determine the efficacy of RUX or FOS to reduce the proportion of patients suffering clinically significant oxygen desaturation
- Determine the efficacy of RUX or FOS to reduce the need for renal replacement therapy
- Determine the efficacy of RUX and FOS to reduce the incidence of venous thromboembolism COVID-19 pneumonia
- Determine the efficacy of RUX and FOS to improve the severity of COVID19 pneumonia on a modified
   WHO COVID19 Ordinal Scale
- Determine the efficacy of RUX or FOS to reduce the level of inflammatory biomarkers
- Determine the efficacy of RUX or FOS to reduce blood ferritin, CRP, LDH and D-dimer
- Determine the efficacy of RUX or FOS to reduce the level of serum creatinine.
- Determine the efficacy of RUX or FOS to reduce duration of hospital admission
- Evaluate the safety of RUX and FOS for COVID19 pneumonia

IRAS: 282552 Page **21** of **57** 

[figure not shown]

- Determine the impact of RUX or FOS to reduce the development of the post-acute COVID-19 syndrome
  in patients who presented with mild-moderate COVID-19 pneumonia
- Determine the impact of RUX or FOS on long term (12-18 months) survival
- Determine the ability of RUX or FOS to reduce the development of the post-acute COVID-19 syndrome
  in patients who presented with mild-moderate COVID-19 pneumonia
- Assess impact of signal inhibitors (RUX or FOS) on health related quality of life at 6 and 12, 18 months post COVID-19

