2.7 Descriptive statistics for outcome measures

The proportion of participants with the primary outcome of WHO COVID- $19 \ge 5$ by day 14 will be summarised by treatment arm and repeated for day 28. This will be undertaken for stage I and stage II.

In addition, the proportion of participants experiencing each of the components of the WHO COVID-19 severity scale score (mortality, invasive ventilation plus organ support (renal replacement therapy, ECMO or inotropic support), invasive ventilation, non-invasive ventilation including CPAP and high flow nasal oxygen) at any point up to day 14 (repeated up to day 28) will be summarised by treatment arm. This will be undertaken for stage I and stage II.

Trajectories of mean (SD) grades over time by treatment arm will also be plotted. This will be undertaken for stage II only.

Time spent at each of the components will be summarised as medians and IQRs by treatment arm. This will be undertaken for stage II only.

All stage 1 analysis of the WHO COVID-19 grades will be completed by the independent statistician in Newcastle University to ensure the trial statistician remains blind and only DMC members will see these results.

Inflammatory markers CRP, LDH, ferritin, D-dimer, and serum creatinine values will be summarised by treatment arm over time and presented as means (SD) and median (IQR). This will be undertaken for stage II

Summaries (means (SD) and median (IQR)) of length of stay will be tabulated amongst those that do not withdraw or die. This will be undertaken for stage II

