3.1 Primary outcome of the main study - Modified WHO grading

3.1.1 Definition of the primary outcome

The proportion of participants progressing from mild to severe COVID-19 pneumonia within 14 days. Where severe COVID-19 pneumonia is defined by a modified WHO COVID-19 Ordinal Score ≥ 5 (on the 9 point scale), comprising the following indicators of disease severity: Death (9) OR Requirement for invasive ventilation plus organ support (8) Requirement for invasive ventilation (7) OR Requirement for non-invasive ventilation including CPAP or high flow oxygen (6) OR O₂ saturation < 90% on \geq 60% inspired oxygen (5). These are captured in the database as follows:

Modified WHO COVID-19 Ordinal Score	Database
(9) Death	
(8) Requirement for invasive ventilation plus organ support	Has the patient required renal replacement therapy? OR Has the patient required ECMO? OR Has the patient required inotropic support? AND Has the patient required intubation and mechanical ventilation?
(7) Requirement for invasive ventilation	Has the patient required intubation and mechanical ventilation?
(6) Requirement for non-invasive ventilation including CPAP or high flow oxygen	Has the patient required NIV, CPAP or high flow nasal oxygen?
(5) O ₂ saturation < 90% on ≥60% inspired oxygen	Has the patient's oxygen saturation been < 90% on 60% inspired oxygen?

3.1.2 Statistical model at stage 1

The stage one primary analysis will consist of fitting two separate binomial regression models for the RUX vs SOC and FOS vs SOC comparisons in order that we can undertake an adjusted analysis using a propensity score approach. Specifically a generalized linear model with WHO COVID-19 status (<5 or ≥ 5) as the outcome and treatment group as a covariate. We will adjust the treatment effect for the

following prespecified covariates using a propensity score approach. The propensity score model will include:

- baseline WHO COVID-19 score (3 or 4)
- age ($<65 \text{ or } \ge 65$)
- receipt of dexamethasone (prior randomisation or up to 1 day post randomisation)
- receipt of tociluzimab (prior randomisation or up to 1 day post randomisation)

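### The ventilation endpoints in SAP 3.2.3 have no rule for death without support, so the odds ratio can favour a drug that only shifts patients from ventilation to unventilated death

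*SAP*

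**What the plan says.** Protocol 2.2 frames the objectives as need for support, for example: "Determine the efficacy of RUX or FOS to reduce the need for invasive ventilation and/or ECMO". A parallel objective covers non-invasive ventilation.

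SAP 3.2.3 carries these out with single yes/no items in the logistic model of SAP 3.1.3: "The following outcomes will be examined at day 14 and day 28 by replacing the primary outcome in the main analysis model". Death is a separate line in the same list. On missing data the section adds: "Each model will be fitted on complete cases and no imputation of missing values or sensitivity analysis will be undertaken".

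The items record whether support was ever needed. The database question in SAP 3.1.1 is "Has the patient required NIV, CPAP or high flow nasal oxygen", with a matching question for intubation. SAP 2.7 counts components "at any point up to day 14 (repeated up to day 28) will be summarised by treatment arm".

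Protocol 2.1 explains that the scale was modified with an extra severe grade that "allows the capture of clinical deterioration in patients for whom escalation in organ support is not offered".

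The SAP has a rule for early discharge on the primary outcome (3.1.2) and for death in the length-of-stay analysis (3.2.4). Neither document has a rule for death on the ventilation items.

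**The concern.** A patient can have no recorded ventilation by recovering or by dying without it, and a bare yes/no item scores these the same. Death without ventilation is foreseeable here, because Protocol 2.1 expects patients who are not offered escalation. The non-invasive item has a second gap: a patient who goes from face mask straight to intubation never needed non-invasive support and is also a no.

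The objectives concern reduced need. If an arm has less ventilation only because more of its patients die before or without it, need has not fallen, yet the odds ratio would say so. The trial is open label, so escalation decisions could also differ by arm.

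**Working it through.** **Plan's own figure.** The documents give no rate, effect or power for the ventilation endpoints, so there is nothing to reproduce on this point. The primary-endpoint design reproduces: about 89.4% to 90.8% joint power for 144 to 152 per arm, against the stated 90%. This point does not touch it.

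**Inputs**
- From the documents: 152 per arm (SAP 1.5.2); yes/no coding with no rule for death (SAP 3.2.3); ever-required items (SAP 3.1.1, 2.7).
- Assumed: on standard of care 15% are ventilated and 5% die unventilated. The drug only moves patients from the first group to the second. Neither document gives these rates.
- Alternative assumption: 30% ventilated. Protocol 1.3 says around 30% of hospitalised patients come to need ventilatory support. That figure is not specific to invasive ventilation, so it is only a loose anchor.

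**Formulas.** With v the proportion ventilated (0 = standard of care, 1 = drug), OR = [v1/(1−v1)] / [v0/(1−v0)]. The 95% CI is exp(ln OR ± 1.96 × SE), with SE² = 1/(n·v0) + 1/(n·(1−v0)) + 1/(n·v1) + 1/(n·(1−v1)). These are crude odds ratios; the SAP model is adjusted.

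**Main case, 5-point shift from 15%**
- Ventilation item: (0.10/0.90)/(0.15/0.85) = 0.63, on 22.8 against 15.2 expected patients.
- SE² = 1/22.8 + 1/129.2 + 1/15.2 + 1/136.8 = 0.1247, so SE = 0.353 and the CI is 0.32 to 1.26.
- Ventilation or death: 0.15 + 0.05 = 0.20 and 0.10 + 0.10 = 0.20, OR 1.00.
- Unventilated deaths dropped as incomplete: 0.15/0.95 = 15.8% and 0.10/0.90 = 11.1%, OR 0.125/0.1875 = 0.67.

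**Range over the assumptions**

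| Ventilated, SOC to drug | Unventilated death | Ventilation OR (95% CI) | Ventilation or death | OR with those deaths dropped |
|---|---|---|---|---|
| 15% to 10% | 5% to 10% | 0.63 (0.32–1.26) | 20% v 20%, OR 1.00 | 0.67 |
| 15% to 5% | 5% to 15% | 0.30 (0.13–0.70) | 20% v 20%, OR 1.00 | 0.33 |
| 30% to 25% | 5% to 10% | 0.78 (0.47–1.29) | 35% v 35%, OR 1.00 | 0.83 |
| 30% to 20% | 5% to 15% | 0.58 (0.34–0.99) | 35% v 35%, OR 1.00 | 0.67 |

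With no shift, every odds ratio is 1.00.

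**Non-invasive item.** Assume 35% on standard of care and 30% on drug, with the 5 points moved to direct intubation or to death without non-invasive support. Then (0.30/0.70)/(0.35/0.65) = 0.80 (95% CI about 0.49 to 1.29). Grade 6 or worse is unchanged, because the moved patients still count.

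**Who is not affected.** A patient who goes from non-invasive support to intubation has already answered yes to the non-invasive question. A grade 8 patient is by the SAP 3.1.1 definition intubated, so remains a yes for invasive ventilation.

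**The case against.** The strongest reply is that death is already counted where it matters. It is a failure in the primary outcome and its 28-day version (SAP 3.1.1, 3.2.1), the worst category in the ordinal model (3.2.2), and modelled in its own right in the list that holds the ventilation items. In the main case unventilated death rises from 5% to 10% (OR 2.11), so someone reading the rows together could be warned.

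Much of this stands, and it keeps the point to secondary endpoints. It does not answer the need-for-ventilation objectives:
- Grade 5 or worse pools desaturation and non-invasive support with intubation and death.
- The ordinal model as written covers days 1, 7 and 14 and gives one odds ratio across all cut-points.
- No planned analysis estimates invasive ventilation or death, or non-invasive support or worse.
- The mortality row counts all deaths, so how far it moves depends on mortality among ventilated patients, which must be assumed. If none of them die, the main case gives 5% against 10%. At 50% it gives 0.05 + 0.5 × 0.15 = 12.5% against 0.10 + 0.5 × 0.10 = 15.0%. At 90% (Protocol 12.3 cites a cohort above 90%) it gives 18.5% against 19.0%, which would hardly show.

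It is also fair to say that the illustration is a worst case, since the drug does nothing but convert ventilation into death; that both 5-point intervals for invasive ventilation include 1; and that the SAP sets a significance threshold only for the primary outcome. The proposed outcomes would not remove the influence of open-label escalation decisions either, because they still contain them.

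Three stronger readings are tempting, and the documents do not support them:
- A reader might infer that anyone who passes beyond non-invasive support counts as a success. The ever-required wording rules that out.
- A reader might infer that the SAP codes unventilated deaths as no. It is silent; that is only the natural reading.
- A reader might infer that the scale was modified to deal with unventilated deaths. Protocol 2.1 describes capturing deterioration, and the added grade is a desaturation grade.

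**Conclusion.** The concern holds for the two ventilation endpoints. With no rule for death, their odds ratios can favour a drug that has reduced nothing, whether unventilated deaths are scored as no or dropped. Under the assumed 5-point shifts in invasive ventilation the apparent effect is an odds ratio of 0.63 to 0.78 against a true 1.00 for ventilation or death. Both intervals include 1. Assumed 10-point shifts give 0.30 to 0.58, with intervals that exclude 1. The direction follows from the coding; the size rests on assumed rates.

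A reader might infer that the primary result or the trial's power is in doubt. Neither is: the primary outcome includes death. This is a cheap improvement to secondary analyses.

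**What to change.** In SAP 3.2 and 3.2.3:
- Add two modelled outcomes, at any time up to day 14 and up to day 28: grade 6 or worse (non-invasive support or worse, including death) and grade 7 or worse (invasive ventilation or death). Use the model of SAP 3.1.3.
- Base conclusions on the need-for-ventilation objectives on these two outcomes.
- State how deaths without support, and intubations without prior non-invasive support, are coded on the single items.
- Keep reporting the single items beside mortality. Protocol 3.3 names them as endpoints for comparison between arms, so they need not be reduced to descriptive counts.

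The cost is SAP wording. The data are already collected and the model is unchanged. The downside is a few more secondary analyses that overlap and are correlated.
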